10.3.6 At 6 months post-procedural follow-up

The tests/observation at 6 months post-procedural follow-up should be performed at 182 days post-procedural visit (\pm 30 days) to collect the data on the following items.

- NYHA classification of cardiac performance (see Section 30 "GLOSSARY")
- CCS status of stable angina (see Section 30 "GLOSSARY")
- Neurological examination (to be performed only for patients diagnosed with a stroke after the procedure)
 - NIHSS (see Appendix 1)
 - mRS (see Appendix 2)
 - * Neurological assessment should be performed by a neurologist, neurosurgeon, or a physician who is able to perform appropriate assessment.
- Blood pressure (systolic, diastolic)
- 12-lead ECG
- Chest X-ray
- Head CT (to be performed only for patients diagnosed with a stroke after the procedure)
- Clinical laboratory test
 - Hematology
Red blood cell count, hemoglobin, hematocrit, platelet count, white blood cell count, differential white blood cell count (neutrophil, lymphocyte, monocyte, eosinophil, basophil)
 - Biochemistry
Sodium, potassium, creatinine, urea nitrogen, albumin, total bilirubin, CRP, GOT(AST),

- 91 -

- GPT(ALT), LDH, hemoglobin A1c, glycated albumin, phosphate, calcium
- Coagulation
 - Prothrombin time, activated partial thromboplastin time
- Cardiac enzyme
 - CK and troponin, or CK-MB and troponin
- Echocardiography

Perform echocardiography in reference to the Echo Core Laboratory Procedure to measure/evaluate the following items. The resulted echocardiographic images should be submitted to the Echo Core Laboratory.

[Measurements/endpoints]

Cardiac output, aortic valve pressure gradient (mean/maximum), EOA, EOA_i[†], aortic valve regurgitation (severity/regurgitation site), maximum blood flow rate, LVEF, left ventricular mass, LVMI[†]

 - * Baseline BSA values must be used for calculation of EOA_i and LVMI.
- QOL questionnaire
 - EuroQOL (see Appendix 4)
 - SF-12 (Appendix 5)
- Anticoagulant/antiplatelet drugs
- Other concomitant medication/therapy
- AE/device deficiency

For a patient who has suffered a stroke, mRS must be evaluated within 30 to 90 days and beyond 90 days as earlier as from the onset of stroke.

10.3.7 At 1 year post-procedural follow-up observation

The tests/observation at 1 year post-procedural follow-up should be performed at 365 days post-procedural visit (± 30 days) to collect the data on the following items.

- NYHA classification of cardiac performance (see Section 30 “GLOSSARY”)
- CCS status of stable angina (see Section 30 “GLOSSARY”)
- Neurological examination (to be performed only for patients diagnosed with a stroke after the procedure)
 - NIHSS (see Appendix 1)
 - mRS (see Appendix 2)

* Neurological assessment should be performed by a neurologist, neurosurgeon, or a physician who is able to perform appropriate assessment.
- Blood pressure (systolic, diastolic)
- 12-lead ECG

- 92 -

- Chest X-ray
- Head CT (to be performed only for patients diagnosed with a stroke after the procedure)
- Clinical laboratory test
 - Hematology
 - Red blood cell count, hemoglobin, hematocrit, platelet count, white blood cell count, differential white blood cell count (neutrophil, lymphocyte, monocyte, eosinophil, basophil)
 - Biochemistry
 - Sodium, potassium, creatinine, urea nitrogen, albumin, total bilirubin, CRP, GOT(AST), GPT(ALT), LDH, hemoglobin A1c, glycated albumin, phosphate, calcium
 - Coagulation
 - Prothrombin time, activated partial thromboplastin time
 - Cardiac enzyme
 - CK and troponin, or CK-MB and troponin
- Echocardiography

Perform echocardiography in reference to the Echo Core Laboratory Procedure to measure/evaluate the following items. The resulted echocardiographic images should be submitted to the Echo Core Laboratory.

[Measurements/endpoints]

Cardiac output, aortic valve pressure gradient (mean/maximum), EOA, EOA_i[†], aortic valve regurgitation (severity/regurgitation site), maximum blood flow rate, LVEF, left ventricular mass, LVMI[†]

 - * Baseline BSA values must be used for calculation of EOA_i and LVMI.
- QOL questionnaire
 - EuroQOL (see Appendix 4)
 - SF-12 (Appendix 5)
- Anticoagulant/antiplatelet drugs
- Blood purification

Investigate the latest dialysis prior to the 1 year post-procedural follow-up visit.
- Other concomitant medication/therapy
- AE/device deficiency

For a patient who has suffered a stroke, mRS must be evaluated within 30 to 90 days and beyond 90 days as earlier as from the onset of stroke.

10.3.8 Years 2 through 5 annual post-procedure visits

The tests/observation at 2 to 5 years post-procedural follow-up should be performed within the permissible time windows shown in Section 10.1 “Test/observation schedule” to collect the data on the following items.

- 93 -

- NYHA classification of cardiac performance (see Section 30 “GLOSSARY”)
- CCS status of stable angina (see Section 30 “GLOSSARY”)
- Echocardiography

Perform echocardiography in reference to the Echo Core Laboratory Procedure to measure/evaluate the following items. The resulted echocardiographic images should be submitted to the Echo Core Laboratory.

[Measurements/endpoints]

Cardiac output, aortic valve pressure gradient (mean/maximum), EOA, EOA_i[†], aortic valve regurgitation (severity/regurgitation site), maximum blood flow rate, LVEF, left ventricular mass, LVMI[†]

 - * Baseline BSA values must be used for calculation of EOA_i and LVMI.
- QOL questionnaire
 - EuroQOL (see Appendix 4)
 - SF-12 (Appendix 5)
- Anticoagulant/antiplatelet drugs
- AE/device deficiency

10.3.9 At trial discontinuation and unscheduled visits

When a subject enrolled in continued access registry discontinues the trial, and if the subject made an unscheduled visit other than those specified in the protocol for necessity as specified in Section 10.2.9, collect the data in accordance with Section 10.2.10.

- 94 -

11 ADVERSE EVENT/DEVICE DEFICIENCY

11.1 Definition of Adverse Events

An AE is any untoward medical occurrence, unintended disease or injury, or untoward clinical signs (including abnormal laboratory findings) in subjects, users, or other persons, whether or not related to the study device. However, for an event occurred in persons other than the subjects, it should be limited to an event suspected to be associated with the use of the study device.

The observation period for AEs will be from the start of the study procedure through to the final follow-up observation visit. A disease developed between the time of informed consent and the start of the study procedure, which has not recovered at the start of the study procedure, should be handled as a pre-procedural complication.

11.2 Definition of Serious Adverse Events

An SAE is an event applicable to the followings, in accordance with the PMD Act Enforcement Regulations Article 274-2, irrespective of causal relationship to the study device.

- (a) Death
- (b) Those that may lead to death
- (c) Those requiring inpatient hospitalization or prolongation of existing hospitalization for treatment
- (d) Disability
- (e) Those that may lead to disability
- (f) Serious cases in accordance with those in (a) to (e)
- (g) Any congenital disease or abnormality in the offspring of a treated patient

However, hospitalization without a newly developed AE or aggravated pre-procedural complication as shown in the followings is not regarded as an SAE, not requiring reporting to the sponsor.

- Hospitalization for treatment scheduled before the procedure (e.g.: hospitalization for surgery for pre-procedural complication that became possible due to improvement in the heart condition)
- Hospitalization for management (e.g.: regular checkup, hospitalization for examination, educational hospital admission)
- Admission to a rehabilitation facility

If an SAE is found, the investigators should take appropriate actions, and immediately report to the sponsor (see Section 11.5 “Serious Adverse Events Reporting”).

- 95 -

11.3 Adverse Events Associated with Laboratory Test Abnormal Variations

If any abnormal variations from baseline are found in the laboratory tests, blood pressure, and ECG as specified in the protocol, and if the value is applicable to the definition of SAE, or if the principal investigator or subinvestigators judges the value as an AE, the event should be handled as an AE. Also for a clinically important abnormal finding is found in the test items not specified in the protocol, and if the finding is applicable to the definition of SAE, or if the principal investigator or subinvestigators judges the finding as an AE, the finding should be handled as an AE.

11.4 Device Deficiencies

A device deficiency is defined as the failure of a device to meet its quality, safety, and performance specifications, such as damage and or malfunctioning, regardless of being associated with the design, supply, storage, or used.

11.5 Serious Adverse Event Reporting

If an SAE or defect that may cause an SAE is found after the start of the study procedure, the principal investigator or subinvestigators should take appropriate actions in accordance with the followings.

- (1) The principal investigator or subinvestigators should take appropriate actions for the subject, and regardless of the causal relationship to the study device, immediately report the SAE or defect that may cause an SAE to the sponsor orally, via telephone, e-mail, or FAX.
- (2) The investigator (if unavoidable, the subinvestigator under instructions from the investigator) should immediately report the details to the director of the study site and sponsor by forms such as "Report of serious adverse events".
- (3) If an event that was assessed as non-serious at the time was reassessed as serious later by additional information, etc., the investigator should take the above-mentioned actions (1) to (2).

After receiving the report from the principal investigator or subinvestigators, the sponsor should take the following actions.

- (4) If the sponsor is aware of any defect unforeseeable from the Investigational Devices Brochure among SAEs or failure that may cause an SAE, the sponsor should immediately report it to the investigators and directors of all study sites.
- (5) The sponsor will report a list of cases with an SAE that is suspected to be associated with the use of the study device or defect that may cause an SAE to the investigator and director of the study sites annually starting from the day of first notification of the study plan and within 3 months after the due

- 96 -

Choose either one of the following 3 actions taken for the study device:

1. No measures taken for the THV
2. Valve explants
3. Other action

(f) Other measures taken:

Record the other measures taken by the following classification:

1. No
2. Yes (measures taken)

(g) Outcome:

Choose either one of the following 6 outcomes for the AE:

1. Recovered
2. Resolving
3. Not recovered
4. Recovered with sequelae
5. Death
6. Unknown

(h) Cause of death (only AEs with outcome of death):

If the outcome of an AE is death, assess the cause of death by the following classification: See Section 30 "GLOSSARY - Death".

1. Cardiovascular death
2. Non-cardiovascular death

(i) Date of outcome (date of the clinical course was confirmed):

Enter the date of the outcome was determined. For a death case enter the date of death, and for laboratory test abnormality enter the date of consultation or test as the date of outcome. If assessed as not recovered, regardless of whether or not related to the study device or study device implantation procedure, except for irreversible AEs or exacerbation of pre-existing complication, the event should be followed up until recovery as a general rule and make an additional report. If a persistent, irreversible AE, or exacerbation of pre-existing complication is determined to be unnecessary to perform follow-up investigation until recovery, enter the assessment in the comment field of the eCRF.

(j) Causal relationship to the study device and study procedure:

Assess the causal relationship to the study device or study procedure by the following classification:

- Definitely related: Applicable to any one of the following a) to c)
- a) Has a temporal relationship

- 98 -

date of the annual reporting period.

- (6) In accordance with the PMD Act Enforcement Regulations Article 274-2, the sponsor should promptly report an SAE or defect that may cause an SAE to Minister of Health, Labour and Welfare.

11.6 Records of Adverse Events

In the event of an AE, it should be recorded in the eCRF in accordance with the followings.

- (1) The investigators should enter all AEs occurred during follow-up observation period in this clinical trial in the eCRFs. The investigators should enter the name of AEs. However, an extremely severe symptom is found in the diagnostic class, it should be entered as a separate event from the original diagnosis. If a definitive diagnosis cannot be clearly established, individual signs or symptoms should be recorded in the eCRF within 10 working days as a general rule.
- (2) The principal investigator or subinvestigators must confirm the outcome of the AE found in a subject, regardless of the causal relationship to the study device.
- (3) If an AE is found, the investigators should enter the followings in the eCRF.
 - (a) Event:

Enter the name of diagnosis as much as possible. If a definitive diagnosis cannot be clearly established, enter the signs or symptoms.
 - (b) Date of onset:

For subjective symptoms, enter the date of onset or exacerbation. For AEs based on the laboratory test abnormal variations, enter the date of consultation or test.
 - (c) Severity:

The severity of AEs will be assessed by the following 3 scales.

Mild: With signs or symptoms that do not interfere with daily activities, or transient not requiring treatment with no secondary disorders

Moderate: Interferes with daily activities, or requires symptomatic treatments

Severe: With symptoms causing a significant pain, which enables to lead daily life, or requiring treatments
 - (d) Severity:

The severity of AEs will be assessed by the following classification. For definition of SAEs, see Section 11.2 "Definition of Serious Adverse Events".

 1. Serious
 2. Non-serious
 - (e) Measures taken for the study device:

- 97 -

- b) The AE abates upon completion of device application or implantation procedure
- c) The AE cannot be clearly explained by the subject's condition or pre-procedural complication

Possibly related: There may be a temporal relationship between the AE and the study device or implantation procedure, or the subject's condition can be reasonably explained.

Possibly unrelated: The temporal relation is unlikely between the AE and the study device or implantation procedure.

Unrelated: There is no relation between the AE and the study device or implantation procedure

Except for events assessed as "Unrelated", handle AEs as with the relationship to the study device or study procedure.

(k) Reason for the assessment result of "Unrelated" to the study device or study procedure:

For AEs that were assessed as "Unrelated" to the study device or study procedure, enter the reason for the assessment result by the following classification:

1. An event associated with physiological factors
2. A pre-existing event associated with the primary disease or exacerbation of complication
3. A transient and accidental event
4. An event associated with concomitant drug or concomitant therapy
5. Other

(l) Comment:

Enter the rationales for the judgment of the causal relationship of AEs to the study device or study procedure and the rationales for the judgement of abnormal laboratory test variations as an AE..

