15.1.2 Statistical analysis plan and statistical method

Mortality at 1 year post-procedure, the primary endpoint, will be analyzed in the AT analysis set to verify the non-inferiority of EWJ-003 therapy to the standard therapy. The non-inferiority test will be performed

- 104 -

made and reasons for the changes, and the Statistical Analysis Plan should be revised.

All deviations from the Statistical Analysis Plan should be described in the Study Report.

- 106 -

using one-sided Fisher's exact test, and at one-sided significant level of 0.05 if the 95% CI upper limit for the mortality at 1 year post-procedure is lower than the PG (45%), non-inferiority of EWJ-003 therapy to the standard therapy would be verified.

No statistical tests will be conducted for the secondary endpoints, but evaluate by descriptive statistics. The secondary valve performance endpoints based on the echocardiographic evaluation will be analyzed in the VI analysis set, and other secondary endpoints. Other data including subject background and baseline characteristics, and procedure information, etc. will be summarized by descriptive statistics.

All statistical analyses will be performed for, in addition to the entire analysis sets, each approach of TF, TA, and TAO. For continuous variables, the number of measurements, mean, standard deviation, median, quartile, minimum, maximum, and 95% CI of the mean will be calculated. On the other hand, for categorical variables, the number of samples (n), percentage (%), and for binary variables 95% CI will be calculated. For the primary endpoint and secondary safety and efficacy endpoints, the cumulative incidence will be calculated by Kaplan-Meier estimates as needed.

The detailed statistical analysis plan and statistical method are included in the Statistical Analysis Plan.

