21 DIRECT ACCESS TO SOURCE DOCUMENTS

21.1 Identification of Source Documents

Source documents are records required for reproduction and evaluation of the course of the trial, such as subject's medical records, the study device use records, etc. Of the data recorded in eCRFs, records of the following items in the eCRFs may be handled as source documents.

- (1) Descriptions of AEs (severity, seriousness, causality, outcome, cause of death, treatments given, and comments)
- (2) Descriptions of defects (name of defect, detailed information on defect)
- (3) Date and reason for discontinuation
- (4) Follow-up investigation of subjects with missing visits
- (5) Descriptions of concomitant drug/therapy
- (6) Clinical decisions and views of the principal investigator or subinvestigators

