Quantitative evaluation [blood flow independent]																																						
Aortic flow velocity coefficient by continuous wave Doppler method	> 0.35	0.35 - 0.25	< 0.25																																			
EOA (cm ²) [BSA ≥ 1.6 cm ²]	> 1.1	1.1 - 0.8	< 0.8																																			
EOA (cm ²) [BSA < 1.6 cm ²]	> 0.9	0.9 - 0.6	< 0.6																																			
As-treated analysis set	A subject population consisting of subjects who were enrolled in this clinical trial and implantation of the study device was initiated is defined as as-treated (AT) analysis set.																																					
Bleeding	
Bleeding can be classified into life-threatening or disabling, severe, and mild by severity.
 
 Life-threatening or disabling bleeding 
 When applicable to any one of the followings: 
 Fatal bleeding (BARC Type 5) Bleeding of major organs (BARC Types 3b and 3c, including intracranial hemorrhage, intramedullary hemorrhage, intraocular hemorrhage, pericardial bleeding requiring pericardial puncture, and muscle hemorrhage with compartment syndrome. Hypovolemic shock or bleeding that induced severe 	VARC-2																																				

Term	Definition	Reference/rationale
	
hypotension requiring vasoconstrictors or surgery.
 
 A decrease in hemoglobin ≥ 5 g/dL, or apparent bleeding with transfusion of whole blood preparation or red cell product ≥ 4 units* (BARC Type 3b) 
 Severe bleeding (BARC Type 3a) 
 Not applicable to the definition of life-threatening or disabling bleeding, and any one of the following is observed: 
 Bleeding with a decrease in hemoglobin ≥ 3.0 g/dL Bleeding with transfusion of 2 or 3 units whole blood preparation or red cell product Bleeding causing hospitalization or a permanent injury Bleeding requiring surgery Mild bleeding (BARC Type 2 or 3a, severity dependent) 
 Not applicable to the definition of life-threatening or disabling bleeding or severe bleeding, and all bleedings assessed as of clinical significance (e.g.: access site hematoma) 
* Considering a predicted increase in hemoglobin of 1 g/dL per unit of general red cell preparation, the reduced hemoglobin level may be estimated
	

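### The three adverse-event severity grades in Section 11.6 overlap, so a treated event cannot be given a single grade; the effect is confined to the recorded severity field and summaries built on it

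*Combined protocol and SAP*

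**What the plan says.** Section 11.6(3)(c) introduces the scale with "The severity of AEs will be assessed by the following 3 scales" and then defines three grades.

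- The highest grade, which names treatment without qualification, is worded "Severe: With symptoms causing a significant pain, which enables to lead daily life, or requiring treatments".
- The middle grade, which names only one kind of treatment, is worded "Moderate: Interferes with daily activities, or requires symptomatic treatments".
- The lowest grade, which mentions treatment only in its second limb, is worded "Mild: With signs or symptoms that do not interfere with daily activities, or transient not requiring treatment with no secondary disorders".

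No rule says which grade to record when more than one applies, and the Section 30 glossary has no general AE severity definition. The next item, (3)(d), is also headed as severity and opens "The severity of AEs will be assessed by the following classification. For definition of SAEs, see Section 11.2", although its two options are serious and non-serious. Section 21.1 treats these as separate fields and allows the electronic case report form (eCRF) entry itself to be the source document: "Descriptions of AEs (severity, seriousness, causality, outcome, cause of death, treatments given, and comments".

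**The concern.** An ordinal safety grade is useful only if an event maps to one level. Here the limbs within each grade are joined by *or*, and the same feature, treatment, appears in more than one grade. The functional limb of Severe also runs the wrong way: as written, significant pain compatible with daily life qualifies, while untreated pain that prevents daily life does not.

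At stake is the consistency of one field recorded for every AE from the start of the procedure to the final follow-up visit, up to 5 years. Two investigators who both follow the text can enter different grades for the same event. Little in the plan would catch this. The eCRF entry may be the source, so a monitor may have nothing independent to compare it with. The event committee in Section 13.1 reviews only deaths and strokes up to 1 year. With 30 subjects in the main cohort and at most three sites (Synopsis), a difference in reading between sites could show in a table of AEs by severity.

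**Working it through.** The plan states no figure on this point, so there is none to reproduce. The check is whether the definitions give each event exactly one grade.

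**Coding the text (Section 11.6(3)(c)).**

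- Mild = no interference with daily activities, OR (transient AND untreated AND no secondary disorder). The no-treatment condition sits only in the second limb.
- Moderate = interference, OR symptomatic treatment.
- Severe = significant pain with daily life still possible (*enables*, taken literally), OR any treatment.

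**Profiles.** Interference (none / some / cannot lead daily life) × treatment (none / symptomatic / other) × transient (yes / no) × secondary disorder (yes / no) × significant pain (yes / no) = 3 × 3 × 2 × 2 × 2 = 72. Of these, 3 × 2 × 8 = 48 are treated and 24 are untreated.

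**Treated profiles.** The result is the same whichever way *enables* is read.

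| Interference | Treatment | Profiles | Grades met |
|---|---|---|---|
| None | Symptomatic | 8 | Mild, Moderate, Severe |
| None | Other | 8 | Mild, Severe |
| Some, or cannot lead daily life | Either | 32 | Moderate, Severe |

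So 8 profiles meet three grades, 40 meet two, and none of the 48 meets exactly one.

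**All 72 profiles.**

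| Grades met | *Enables* as written | Read as preventing daily life |
|---|---|---|
| Mild only | 4 | 8 |
| Moderate only | 9 | 9 |
| Severe only | 0 | 0 |
| Mild and Moderate | 3 | 3 |
| Mild and Severe | 12 | 8 |
| Moderate and Severe | 35 | 35 |
| All three | 9 | 9 |
| Total | 72 | 72 |

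A single grade results in 4 + 9 = 13 of 72 profiles as written and in 8 + 9 = 17 of 72 after reversing *enables*. Correcting that word restores the direction of the functional limb but leaves the overlap, which comes from the bare treatment limb in Severe and the *or* in Mild. No profile is uniquely Severe under either reading.

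These are counts of logical combinations. They are not expected event frequencies.

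**Where the scale reaches.** The primary endpoint is death: "Mortality at 1 year post-procedure, the primary endpoint, will be analyzed in the AT analysis set". Among the Section 9.2.1 safety endpoints, bleeding has its own grading ("Bleeding can be classified into life-threatening or disabling, severe, and mild by severity"), and vascular complications, stroke and myocardial infarction likewise have their own definitions in Section 30. Reporting under Section 11.5 turns on seriousness as defined in Section 11.2. Section 15 names no table of AEs by severity and leaves detail to a separate Statistical Analysis Plan.

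**The case against.** The best case for the plan is that the scale has a natural order that clinicians will follow. Treatment rises from none, to symptomatic, to treatment in general, alongside rising functional impact. *Enables* is very probably a language slip: Section 17 has *evitable* where unavoidable is meant, and Section 11.7 has *result* where *rule* is meant. Few readers would take a line headed Severe to mean that daily life is possible. Item (d) explains itself through its options and its pointer to Section 11.2. Section 16.1 mentions an eCRF input guide and Section 20 requires training; either may hold a rule that cannot be seen here.

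Much of this stands. The slip is likely, though that is an inference. The ordered reading is reasonable, but the text does not state it, and it does not remove the overlap. Suppose Severe requires treatment other than symptomatic, and *enables* is reversed. Then the treated profiles with a single grade are 8 (some interference, symptomatic treatment) plus 4 (cannot lead daily life, symptomatic treatment, no significant pain), or 12 of 48. The other 36 still meet two grades. If the guide or the training settles the matter, the rule belongs in Section 11.6 as well.

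A reader might also infer more than the documents support:

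- *Every treated event must be graded Severe.* The text permits this but does not force it, since each such event also meets Mild or Moderate.
- *A treated asymptomatic finding meets all three grades.* It meets Mild and Severe. Moderate needs interference or symptomatic treatment.
- *A large, quantifiable share of events will be overgraded.* The documents give no proportion of AEs treated. Any figure, such as 60% to 90%, would be an assumption returned as a result.
- *Site readings will dominate the tables.* Neither the split of subjects by site nor the guide is available to show this.

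**Conclusion.** The grades in Section 11.6(3)(c) are not mutually exclusive. A symptomatically treated, non-interfering event meets all three, every other treated event meets two, and the functional limb of Severe runs opposite to its evident intent. This follows from the wording alone and rests on no assumption about event rates. The only assumption is that no tie-break exists outside the documents.

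The consequence is limited to the recorded AE severity field and any summary by severity. The bailout and continued access analyses, which Sections 15.2 and 15.3 say will primarily confirm safety, would share it if they report severity. The primary mortality test, the separately defined secondary safety endpoints and serious-event reporting are unaffected. The text should be corrected because the defect is clear and cheap to remove; it does not put the trial's main conclusion in doubt.

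**What to change.** In Section 11.6(3)(c):

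1. Change *enables* to the sense of preventing daily life.
2. Remove or qualify the bare treatment limb in Severe.
3. Join the Mild conditions so that each event has exactly one grade, or state that the highest grade met is recorded. A highest-grade rule is not enough without step 2, because all 48 treated profiles would then be Severe. Requiring all of Mild's conditions together also needs care: an untreated, non-interfering event that persists could be left with no grade.

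The exact cut-offs are for the sponsor. Running the revised wording through the same 72 profiles would confirm one grade for each.

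Retitle item (d) as seriousness, to match Section 21.1.

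Apply the corrected definition to new entries. Enrollment in the main cohort is closed and the trial is open-label, so anyone regrading earlier events may know the outcome. If earlier events are regraded, use a documented rule, keep the original grade and record the reason; the items for which Section 16.2 requires a stated reason do not include severity.

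The cost is one paragraph of protocol text, a small update to the eCRF guide and some re-entry work. If earlier entries are left alone, summaries by severity will mix two definitions and should say so.
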